#### **5.2.3. Allocation of subjects to assay subsets**

A subset is defined as a group of subjects for which additional assays are planned as compared to other subjects. Approximately 90 subjects per group (approximately 30 children per age stratum per group) will be part of the subset for additional humoral immunogenicity assays. These will be the same subjects as the subjects in the sub-cohort for CMI (refer to [Section 4.2](#)).

### **5.3. Method of blinding**

The blinding level will change in the course of the study:

- **Observer-blind** from study start until the interim analysis that will be conducted when safety, reactogenicity and immunogenicity (including at least anti-GP EBOV data at Day 30) data is available from all subjects up to 30 days after vaccination at Day 0 (refer to [Section 11.11.1](#) for more information on this interim analysis). By observer-blind, it is meant that the vaccine recipient and those responsible for the evaluation of any study endpoint will all be unaware of which vaccine was administered. To do so, vaccine preparation and administration at Day 0 will be done by authorised medical personnel who will not participate in any of the study clinical evaluation assays.

*To ensure blinding of the site staff when preparing and administering the study vaccine details of vaccine management will be defined in a site vaccine management plan before site initiation.*

*(Amended 06 May 2015.)*

- **Single-blind** as of the interim analysis. At the time of the interim analysis, the study will become single-blind to ensure full data availability. By single-blind, it is meant that vaccination centre and sponsor personnel are aware of the treatment assignment but the subject is not.

The laboratory in charge of the laboratory testing will be blinded to the treatment, and codes will be used to link the subject and study (without any link to the treatment attributed to the subject) to each sample.

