**Blinding:**

A procedure in which one or more parties to the trial are kept unaware of the treatment assignment in order to reduce the risk of biased study outcomes.

Observer-blind means that the subject and the vaccination centre and sponsor personnel involved in the clinical evaluation of the subjects are blinded while other study personnel may be aware of the treatment assignment.

Single-blind means that vaccination centre and sponsor personnel are aware of the treatment assignment but the subject is not.

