**5.5.2. Intervals between study visit****Table 6 Intervals between study visits**

Interval	Allowed interval
Screening → Visit Day 0	0 to 30 days
Visit Day 0 → Visit Day 3	3 days
Visit Day 0 → Visit Day 6	6 to 8 days
Visit Day 0 → Visit Day 30	30 to 44 days 
Visit Day 0 → Contact Month 3	3 months ± 30 days
Visit Day 0 → Visit Month 6	6 months ± 30 days 
Visit Month 6 → Visit Month 6 + 6 days	6 to 8 days
Visit Month 6 → Visit Month 6 + 30 days	30 to 44 days 
Visit Month 6 → Contact Month 9	3 months ± 30 days
Visit Month 6 → Visit Month 12	6 months ± 30 days 

 Subjects will not be eligible for inclusion in the according-to-protocol cohort for immunogenicity if they make the study visit outside this interval.

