**5.6.14.1. Diary Card for follow-up adverse events occurring from day 0 to day 6 after vaccination**

Subjects will be followed up for AEs on a daily basis during the 7-day follow-up period after vaccination. During this period, AEs *with the exception of AEs of specific interest (clinical symptoms of thrombocytopenia)* will be recorded on a Diary Card, which will be managed/ completed by the Investigator (at study visits during the 7-day follow-up period), or by a field worker (at home visits during the 7-day follow-up period; on those days that no study visit is planned).

*(Amended 06 May 2015.)*

The home visits will be conducted by a trained field worker under the supervision of the Investigator. In the event that the field worker finds any Grade 3 AE, the child will be brought to the vaccination centre for examination by a study clinician. Any further clinical data, including treatment provided, will be documented on the paper Diary Card and on specific clinic forms and transcribed in eSource. If the physician finds that the child has experienced a SAE, the appropriate measures will be taken to report this (refer to [Section 9.4](#) for instructions on reporting SAEs).

Diary Cards will be checked and verified by the Investigator or his/ her designate before transcription in eSource. The Investigator has a primary responsibility for the data transcribed in eSource. Unresolved AEs will be followed-up by field workers until resolution under the supervision of the Investigator and data will be entered in eSource.

The procedures and frequency of visits will be outlined in an SOP at the vaccination centre.

**5.6.14.2. Unsolicited adverse events occurring from day 0 to day 29 after vaccination and serious adverse event data collection during the entire study duration**

Subjects will be advised to present when unwell. All unsolicited AEs will be captured by passive detection from day 0 up to day 29 after vaccination. All SAEs will be captured during the entire study duration. In order to maximise data completeness, occurrence of events will be discussed and reviewed during the planned study visits.

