#### **Staggered design and IDMC meetings**

No safety concerns have been raised from vaccination with different dosages of the investigational ChAd3-EBO-Z vaccine in healthy adults in the ongoing Phase 1 studies. However, the investigational vaccine has never been administered to children yet. In order to ensure maximum safety for the subjects in this study, vaccination in the study will only start after a favourable outcome of an IDMC review of the safety and reactogenicity data from 100 adults after 1 week follow-up in the study EBOLA Z CHAD3-005. In addition, vaccination at Day 0 will be done in a staggered manner, starting with vaccination of the children in the oldest age stratum. For each age stratum, the IDMC will conduct a review of all available safety data once data is available up to at least 7 days after vaccination of at least 50 subjects (25/ group) in that age stratum. In order to proceed to vaccination of the subjects in the younger age stratum (6 to 12 years of age), possibly with a lower vaccine dose, a favourable outcome of the IDMC review of safety data up to at least 7 days after vaccination from at least 50 subjects (25/ group) in the oldest age stratum needs to be obtained. The same will be done for moving from the 6 to 12 years of age stratum to vaccination of the youngest children (1 to 5 years of age).

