## **11. STATISTICAL METHODS**

### **11.1. Primary endpoints**

- Occurrence of each solicited local and general AE, during a 7-day follow-up period after each vaccination in all subjects, in both groups.
- Occurrence of any unsolicited AE, during a 30-day follow-up period after each vaccination (*i.e.*, the day of vaccination and 29 subsequent days), in all subjects, in both groups.

- Occurrence of haematological (CBC, including differential count and platelet count) and biochemical (ALT, creatinine) laboratory abnormalities at Screening, Day 3, Day 6, Day 30, Month 6, Month 6 + 6 days, Month 6 + 30 days and Month 12 in all subjects in both groups.
- ***Occurrence of clinical symptoms of thrombocytopenia (AE of specific interest), during a 7-day follow-up period after vaccination at Day 0 (i.e., Day 0 up to Day 6), in all subjects, in both groups.***  

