## 4.2. INTERIM ANALYSIS

An unblinded interim analysis will be conducted when safety and immunology data up to Day 30 have been collected for all subjects. All available safety and immunogenicity data in the interim analysis transfer will be included in the interim analysis. As per protocol, the blinded team will be unblinded at the time of the interim analysis and will produce the unblinded interim analysis TLFs.

The cleaning of the 30-day safety data for each subject will be scheduled to be completed prior to the unblinding in order to keep the blind during data cleaning activities.

The interim analysis is planned once the following has been completed:

- GSK's authorization of the following:
  - o SAP. o Relevant TLF shells. o Analysis cohort assignments.
- Immunogenicity data availability:

Document: CHAD3-004-EBO-Z\_Interim\_Final\_SAP\_v2\_0  
 Author: PPD Version Number: 2.0 Version Date: 14JUN2017

Template No: CS\_TP\_BS016 – Revision 3  
 Effective Date: 01May2012

Reference: CS\_WI\_BS005

- o At least the Day 30 anti-GP EBOV data should be available.
- Interim analysis data transfer from Data Management.

The interim analysis data transfer should comply with:

- All the data up to Day 30 is clean:
  - o All outstanding data issues and queries resolved.
  - o All unresolvable data issues documented in the Data Handling Report (DHR), a separate document produced by Data Management.
  - o All coding, for example AEs, is completed. o All reconciliation of vendor data with eSource data completed successfully.
- Any additional data post-Day 30 should be as clean as possible.

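### After the Day 30 interim, site staff who rate adverse events may know which vaccine a child received at Month 6, and the ChAd3-EBO-Z ratings are pooled with blinded Day 0 ratings

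*Protocol*

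**What the plan says.** Protocol Section 5.3, repeated in the blinding bullets of the Synopsis and Section 3, keeps the study observer-blind until an interim analysis held once "data is available from all subjects up to 30 days after vaccination at Day 0", including at least the Day 30 anti-GP results. Then: "At the time of the interim analysis, the study will become single-blind to ensure full data availability". The Glossary defines the new state: "Single-blind means that vaccination centre and sponsor personnel are aware of the treatment assignment but the subject is not". SAP v2.0 Section 4.2 adds, for the CRO statisticians, "As per protocol, the blinded team will be unblinded at the time of the interim analysis".

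Adverse events after both doses are primary endpoints. Section 11.1 lists "Occurrence of each solicited local and general AE, during a 7-day follow-up period after each vaccination in all subjects, in both groups", with a parallel 30-day endpoint for unsolicited events. Section 5.6.14.1 says who makes the record: a Diary Card "which will be managed/ completed by the Investigator (at study visits during the 7-day follow-up period), or by a field worker". Under Section 9.3.3.2 the investigator grades unsolicited events and judges causality for everything except solicited local reactions, which count as related by rule.

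The Month 6 visit falls "6 months ± 30 days" after the child's own Day 0 (Table 6). Section 9.10 sets the order of entry: "vaccination at Day 0 will be done in a staggered manner, starting with vaccination of the children in the oldest age stratum".

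The safety analysis (Protocol 11.8; SAP v2.0 Sections 6.3.1, 15.1.2 and 15.2.2) first presents results by Day 0 treatment. It then pools the ChAd3-EBO-Z doses given at Day 0 and at Month 6 (300 + 300), without a control. Protocol 11.8 asks for results by age stratum and overall.

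**The concern.** The blind changes once for the whole study, while Month 6 arrives child by child, and nothing links the two. After the switch, no text keeps investigators and field workers blind for the Month 6 doses still to come. A rater who knows that a child has just had the investigational vaccine may record more symptoms, grade them higher, or call them related more often.

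Those ratings enter the same pooled ChAd3-EBO-Z tables as Day 0 ratings made blind. Because strata start in age order, the share of unblinded ratings can differ by age, so part of an apparent age difference could reflect what the rater knew. Serious adverse events are exposed too. The SAE tables in SAP v2.0 Section 15.1.5 include relatedness and run to data cut-off (Section 15.1.6), so they take in causality judgements made after the switch.

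The stated reason, full data availability, is met by unblinding those who produce the outputs. SAP v2.0 Section 4.1 already routes unblinded IDMC outputs through a separate statistical team without opening the code to sites.

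**Working it through.** **The plan's own figure.** The documents give no count of Month 6 doses rated after the switch. The nearest stated figure is the precision in Table 22, which reproduces (0/300: 1 − 0.025^(1/300) = 0.0122). It describes a group of 300 before the Month 6 vaccination and does not bear on rater knowledge.

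**Inputs.** From Table 6: Day 30 visit D30 = 30 to 44 days after Day 0; Month 6 visit M6 = 183 ± 30 days (taking 6 months as 183 days), so 153 to 213. From Table 4: 100 children per group per stratum, so 100 Month 6 ChAd3-EBO-Z doses per stratum and 300 in all. Not in the documents, so assumed: the accrual pace, and L, the days from the last child's Day 30 visit to the interim.

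**Condition.** For a child enrolled on day t, with the last child enrolled on day T:
- switch at T + D30 + L
- Month 6 dose at t + M6
- the dose follows the switch if T − t < M6 − D30 − L

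At nominal days (183 and 30) the limit is 153 − L. Over the visit windows it runs from 153 − 44 − L = 109 − L to 213 − 30 − L = 183 − L.

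**Scenarios.** Nominal days, uniform accrual, equal enrolment time per stratum. Strata follow one another, except in the overlapping row, where each takes 60 days and starts 30 days after the one before. Counts are Month 6 ChAd3-EBO-Z doses given after the switch.

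| Accrual (days) | L (days) | Limit 153 − L | Oldest / middle / youngest (of 100 each) | Total of 300 | Youngest share |
|---|---|---|---|---|---|
| 90 | 60 | 93 | 100 / 100 / 100 | 300 | 33% |
| 180 | 30 | 123 | 5 / 100 / 100 | 205 | 49% |
| 180 | 60 | 93 | 0 / 55 / 100 | 155 | 65% |
| 180 | 90 | 63 | 0 / 5 / 100 | 105 | 95% |
| 270 | 60 | 93 | 0 / 3 / 100 | 103 | 97% |
| 270 | 120 | 33 | 0 / 0 / 37 | 37 | 100% |
| 120, overlapping | 120 | 33 | 0 / 5 / 55 | 60 | 92% |
| any | ≥ 153 | ≤ 0 | 0 / 0 / 0 | 0 | – |

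Example, 180 days and L = 60: each stratum takes 60 days. The middle stratum enrolled 60 to 120 days before the last child, and the part inside 93 days is 33/60 × 100 = 55.

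**Doses that straddle the switch.** A dose given before the switch can still have part of its 30-day follow-up after it. With L = 153 and 60-day strata, no dose follows the switch, but 29/60 × 100 = 48 of the youngest stratum's 100 doses straddle it.

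**Effect on the pooled result.** If knowing the vaccine raises a recorded rate by d among affected doses, a pooled rate moves by d × (affected doses / pooled doses). In the 180-day, L = 60 row this is 155/600 = 0.26d overall. By stratum it is 0 for the oldest, 55/200 = 0.28d for the middle and 100/200 = 0.50d for the youngest. The documents give no basis for a value of d.

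**The case against.** The strongest reply is that the plan discloses the change of blind and protects what matters most. Much of this stands.

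- The randomised comparison of solicited and 30-day unsolicited events after Day 0 is collected before the switch, and SAP v2.0 Section 4.2 schedules cleaning of the 30-day safety data before unblinding. This stands in full.
- The laboratory stays blinded and its values are graded by fixed limits. Events of specific interest are collected after Day 0 only. Redness, swelling and fever are measured and graded by cut-offs, local reactions are related by rule, and the children remain blind. This stands, and confines the exposure to subjective solicited symptoms, unsolicited events and non-local causality.
- All analyses are descriptive, and the Day 0 results by stratum give a blinded reading. Symptom lists and redness/swelling scales already differ by age. This stands and limits the seriousness.
- The lag may be long enough that few or no doses follow the switch. The interim waits for clean Day 30 data on every child, several authorisations and ELISA results, and SAP v1.0 Section 14.1.1.1 still awaited assay validation. This is possible, but it leaves rater blinding of primary endpoints to a lag that nobody has specified.
- The site vaccine management plan in Section 5.3 is not confined to Day 0, and unblinded IWRS information is restricted. This helps for Month 6 doses given before the switch, although the sentence separating vaccine staff from evaluation names Day 0 only. It does not help afterwards, when centre personnel are by definition aware.

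**Conclusion.** The point holds as a gap in rater blinding for Month 6 doses given after the interim, and for SAE causality judged after it. Its size is open: 0 to 300 of the 300 Month 6 ChAd3-EBO-Z doses, at most half of the 600 pooled, depending on accrual and lag. In every scenario run the youngest stratum is at least as exposed as an older one. That rests on strata starting in the stated order and filling at a similar pace.

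Three stronger readings go beyond the documents. A reader might infer that many Month 6 doses, mostly in the youngest children, are rated unblinded. Without accrual dates or a lag, neither part can be asserted: the youngest share runs from 33% to 100% where any dose is affected. A reader might also take the switch as a fixed calendar date, but it is triggered by data availability. Finally, a reader might conclude that a concurrent randomised Month 6 comparison is spoiled. SAP v2.0 Sections 15.1.2 and 15.2.2 exclude Month 6 events from the incidence tables unless otherwise specified, and Protocol 11.8 says the pooled data cannot be set against control. For the same reason the Month 6 Nimenrix doses do not add to the 300.

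This is a cheap improvement to a descriptive safety analysis. It does not threaten the Day 0 comparison.

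**What to change.** In Section 5.3, the Synopsis and the Section 3 blinding bullets, state that:
- at the interim only the sponsor/CRO analysis team is unblinded;
- investigators, field workers and everyone else who evaluates an endpoint stay observer-blind until the last Month 6 + 30 days visit;
- vaccine preparation and administration at Month 6 are done by the separate unblinded staff used at Day 0.

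The modification history of SAP v2.0 mentions analyses already prepared for the interim, so the switch may have passed. In that case SAP v2.0 Sections 15.1.2 and 15.2.2 should also present the pooled ChAd3-EBO-Z event tables split by Day 0 versus Month 6 dose, and the Month 6 doses split by whether they were given before or after the switch, overall and by age stratum.

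Cost: protocol wording, or a few extra tables. Separate vaccine staff and restricted IWRS access already exist for Day 0, and emergency unblinding is unchanged. The downside is that vaccine staff stay apart from evaluation at Month 6 and sites see individual codes later.

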#### **5.4. General study aspects**

Supplementary study conduct information not mandated to be present in this protocol is provided in the accompanying manuals. The manuals provide the Investigator and the site personnel with administrative and detailed technical information that does not impact the safety of the subjects.

**5.5. Outline of study procedures****5.5.1. List of study procedures****Table 5 List of study procedures during visits to the vaccination centre (Amended 06 May 2015)**

Type of contact	Visit	Visit	Visit	Visit	Visit	Contact *	Visit	Visit	Visit	Contact *	Visit
Timepoint	Screening 	Day 0 	Day 3	Day 6	Day 30	Month 3	Month 6	Month 6 + 6 days	Month 6 + 30 days	Month 9	Month 12
Informed consent	•										
Informed assent 	•										
RDT for Malaria	•										
Malaria treatment 	•										
Inclusion/exclusion criteria 	•	•									
Demographic data	•										
Medical history 	•	•									
Physical examination (including vital signs  )	• 	• 	0	0	0		•	0	0		0
Pregnancy test 	•	• 					•				
Pre-vaccination body temperature		•					•				
Check contraindications to vaccination		0					0				
Study group and treatment name allocation 		0					0				
Vaccination		•					•				
Recording of administered treatment number		0					0				
30 minutes post-vaccination observation		0					0				
Blood sampling:											
Blood for haematology/ biochemistry	• 		•	•	•		•	•	•		•
Blood for humoral immunity		•			•		•		•		•
Blood for CMI 		•			•		•		•		•
Safety assessment:											
Record solicited AEs (day 0 to day 6)		•	•	•			•	•			
Record unsolicited AEs (day 0 to day 29)		•	•	•	•		•	•	•		
Record AEs of specific interest (clinical symptoms of thrombocytopenia)			•	•							
Record SAEs	• 	•	•	•	•	•	•	•	•	•	•
Record pregnancies		•	•	•	•	•	•	•	•		

**CONFIDENTIAL**

202090 (EBOLA Z CHAD3-004)  
Protocol Amendment 2 Final

Type of contact	Visit	Visit	Visit	Visit	Visit	Contact *	Visit	Visit	Visit	Contact *	Visit
Timepoint	Screening 	Day 0 	Day 3	Day 6	Day 30	Month 3	Month 6	Month 6 + 6 days	Month 6 + 30 days	Month 9	Month 12
Record concomitant medications/ products/ vaccinations 		•	•	•	•	•	•	•	•	•	•
Screening Conclusion	•										
Study Conclusion											•

~ = approximately; **AE** = adverse event; **CMI** = cell-mediated immunity; **CRO** = Contract research organisation; **EVD** = Ebola virus disease; **GSK** = GlaxoSmithKline; **RDT** = *Rapid*

**Diagnostic Test**; **SAE** = serious adverse event

• is used to indicate a study procedure that requires documentation in eSource.

○ is used to indicate a study procedure that does not require automatic transfer of the study data fields from the source database into the study database at the CRO.

\* Home visit by field worker or phone call.

 The Screening visit and the Day 0 visit may take place on the same day (allowed interval 0 to 30 days).

 Refer to [Section 5.6.6](#) for the specific assessments included in the physical examination.

 Only if Visit 1 and Screening take place on a different day.

 Only for women of childbearing potential.

 Only if Visit 1 takes place more than 1 week after the Screening Visit.

 Treatment name allocation with randomisation at Day 0; treatment name allocation without randomisation at Month 6.

 Only for subjects in the sub-cohort for cell-mediated immunity (CMI).

 From Screening to Day 0, only those SAEs that are considered related to study participation or to concurrent use of GlaxoSmithKline (GSK) medication/ vaccine need to be recorded.

 Concomitant medications/ products/ vaccinations as described in [Section 6.7.1](#) and [6.7.2](#) need to be recorded in eSource.

 Only for subjects in the oldest age stratum (13 to 17 year olds) and younger subjects as per local requirements.

 **Subjects diagnosed with Malaria at Screening must receive antimalarial treatment according to local/ national standards (e.g., a 3-day treatment course of artemisinin-based combination therapy), during the Screening period.**

 **Study procedure must be performed at least 5 days after completion of Malaria treatment for all subjects diagnosed with Malaria at Screening.**

**5.5.2. Intervals between study visit****Table 6 Intervals between study visits**

Interval	Allowed interval
Screening → Visit Day 0	0 to 30 days
Visit Day 0 → Visit Day 3	3 days
Visit Day 0 → Visit Day 6	6 to 8 days
Visit Day 0 → Visit Day 30	30 to 44 days 
Visit Day 0 → Contact Month 3	3 months ± 30 days
Visit Day 0 → Visit Month 6	6 months ± 30 days 
Visit Month 6 → Visit Month 6 + 6 days	6 to 8 days
Visit Month 6 → Visit Month 6 + 30 days	30 to 44 days 
Visit Month 6 → Contact Month 9	3 months ± 30 days
Visit Month 6 → Visit Month 12	6 months ± 30 days 

 Subjects will not be eligible for inclusion in the according-to-protocol cohort for immunogenicity if they make the study visit outside this interval.

**5.6. Detailed description of study procedures****5.6.1. Informed consent**

The signed/witnessed/thumb printed informed consent of the subject's parent(s)/ LAR(s) must be obtained before study participation. For subjects in the oldest age stratum (13 to 17 years) and for younger subjects as per local requirements, the signed informed assent of the subject should be obtained in addition to the signed informed consent by his/her parent(s)/ LAR(s). Refer to [Section 5.1](#) for the requirements on how to obtain informed consent as appropriate.

[figure not shown]
